**Figure JAHO.3.2. Illustration of study design for Clinical Protocol I4V-MC-JAHO(e).**

### 3.2. Method of Assignment to Treatment

Different randomization schemes will be used at Visit 2: two during Stage 1 and one during Stage 2. In Stage 1, the first approximately 100 patients who meet all criteria for enrollment will be randomized in a 1:1:1:1 ratio to receive placebo QD, baricitinib 1 mg QD, baricitinib 2-mg QD, or baricitinib 4-mg QD double-blind treatment at Visit 2 (Week 0). After that, up to a maximum of approximately 200 additional patients are anticipated to be randomized during Stage 1, prior to the Decision Point, in a 2:2:3 ratio to receive placebo QD, baricitinib 2-mg QD or baricitinib 4-mg QD. At the Decision Point, baricitinib 4-mg and 2-mg were selected to continue into Stage 2. Therefore, after the Decision Point, patients will continue to be randomized in a 2:2:3 ratio to receive placebo QD, baricitinib 2-mg QD, or baricitinib 4-mg QD. Baseline randomization will be stratified by geographic region (North America, Japan for Phase 2 portion, and North America, Asia, and Rest of World for Phase 3 portion), and duration of current episode at Baseline (less than 4 years versus at least 4 years) for the whole study. Randomization for the randomized withdrawal period will not be stratified. Assignment to treatment groups will be determined by a computer-generated random sequence using an IWRS. The IWRS will be used to assign bottles, each containing double-blind IP tablets, to each patient, starting at Visit 2 (Week 0), and at each visit up to and including Visit 23 (Week 184). Site personnel will confirm that they have located the correct bottles by entering a confirmation number found on the bottle into the IWRS.

This study will be conducted internationally in multiple sites. [Table JAH0.3.1](#) describes how regions will be defined for stratification. Regions may be combined for statistical analyses in the case when one of the region strata fails to meet the required minimum number of 30 patients. The 2 region strata with the least number of patients will then be pooled.

**Table JAH0.3.1. Geographic Regions for Stratification**

Phase 2 portion		Phase 3 portion	
Region	Country	Region	Country
North America	United States	North America	United States
Japan	Japan	Asia	South Korea
		Rest of World	Mexico

## 4. Priori Statistical Methods

### 4.1. Determination of Sample Size

Study JAHO will screen approximately 1035 patients in order to enroll approximately 725 patients over Stage 1 and Stage 2.

Stage 1 aims to enroll a maximum of approximately 300 patients with the first approximately 100 patients randomized in a 1:1:1:1 ratio to placebo QD, baricitinib 1 mg QD, baricitinib 2-mg QD, or baricitinib 4-mg QD and up to a maximum of an additional 200 patients randomized in a 2:2:3 ratio to placebo QD, baricitinib 2-mg QD, or baricitinib 4-mg QD. This sample size will yield approximately 100 randomized and treated patients who will have completed Week 12 (Visit 5) or discontinued early, and who will be used for the conduct of an interim analysis at the Decision Point. The goal of this interim analysis is to select up to 2 doses of baricitinib or to stop for futility based on a pre-specified criteria. The sample size of approximately 100 patients is also sufficient to select at least one efficacious dose at least 80% of the time, based on the said pre-specified criteria.

Stage 2 randomization will begin with a 2:2:3 ratio for placebo QD, baricitinib 2-mg QD, or baricitinib 4-mg QD selected after Decision Point. This study is designed so that approximately 425 patients are randomized in Stage 2. All randomized patients in the Phase 3 portion will be included in the primary efficacy analysis. Hence, approximately up to 625 patients will be eligible for the primary efficacy analysis. This sample size will provide more than 90% power to test the superiority of baricitinib 4-mg to placebo or the superiority of baricitinib 2-mg to placebo in the primary endpoint (the proportion of patients with a SALT  $\leq 20$  at Week 36) based on a 2-sided Fisher exact test, within the original graphical testing scheme, at an initial significance level of 0.04 for 4-mg dose and 0.01 for 2-mg dose. The assumptions used for the power calculation are as follows: 30% response rate for baricitinib 4-mg, 20% response rate for baricitinib 2-mg, and 5% response rate for placebo (Kennedy Crispin et al. 2016; Mackay-Wiggan et al. 2016). The initial alpha allocation in the final graphical testing scheme is presented in Section 4.6.

Patients who achieve a SALT  $\leq 20$  at Week 52 (responders) AND who have remained on the same dose of baricitinib from randomization (Visit 2) to Week 52, will enter the randomized withdrawal, which is meant to evaluate the change in clinical response after treatment withdrawal, and does not account for whether the sample size is sufficient to detect statistical difference between baricitinib and placebo. It is expected that there would be approximately 100 patients eligible for the randomized withdrawal.

### 4.2. General Considerations

This plan describes *a priori* statistical analyses for efficacy, health outcomes, and safety that will be performed.

Statistical analysis of this study will be the responsibility of Eli Lilly and Company (Lilly). The statistical analyses will be performed using SAS® Version 9.4 or a more recent version.

Not all displays described in this SAP will necessarily be included in the CSR. Not all displays will necessarily be created as a “static” display. Some may be incorporated into interactive display tools instead of or in addition to a static display. Any display described in this SAP and not included in the CSR would be available upon request.

Statistical tests of treatment effects and confidence intervals (CIs) will be performed at a 2-sided significance level of 0.05, unless otherwise stated (e.g., graphical multiple testing strategy in Section 4.6).

Data collected at early termination visits will be mapped to the closest scheduled visit number for that patient if it falls within the visit window as discussed in Section 4.2.2. For by-visit summaries, only visits in which a measure was scheduled to be collected will be summarized. Any unscheduled visit data will be included at the patient-level listings. However, the data may still be used in other analyses, including but may not be limited to, shift analyses for safety analyses, change from baseline using modified last observation carried forward (mLOCF) for efficacy analyses, and other categorical analyses including safety.

This SAP also covers the Addendum 4 safety data up to week 248 which will be analyzed in the final database lock (F-DBL). As part of Addendum 4, implemented in Mexico, patients were permitted to continue treatment beyond Week 200, extending until Week 248.

### 4.2.1. Analysis Populations

**Table JAHO.4.1. Analysis Populations**

Population	Description
Phase 2, Week 12 Interim Analysis Set (IAS)	The first approximately 100 randomized and treated patients in Phase 2 portion within Stage 1 who completed Visit 5 (Week 12) assessment or discontinued early. Patients will be analyzed according to the IP to which they were randomized at Baseline (Visit 2).
Phase 2, Week 36 Interim Analysis Set (IAS)	The first approximately 100 randomized and treated patients in Phase 2 portion who completed Visit 8 (Week 36) assessment or discontinued early. Patients will be analyzed according to the IP to which they were randomized at Baseline (Visit 2).
Full Analysis Set (FAS)	All patients enrolled in Phase 3 portion, and who are randomized to baricitinib 4-mg, baricitinib 2-mg, and placebo treatment arms in both Stages 1 and 2 will be included in the FAS. Patients will be analyzed according to the IP to which they were randomized at Baseline (Visit 2).
Modified Full Analysis Set (mFAS) Population	All patients enrolled in Phase 3 portion, and who are randomized to baricitinib 4-mg, baricitinib 2-mg, and placebo treatment arms in both Stages 1 and 2, and received at least 1 dose of IP, will be included in the mFAS. It excludes patients with female pattern baldness and male patients with diffuse AGA a (Grade IV and above) (Norwood 1975) identified at Week 36. Patients will be analyzed according to the IP to which they were randomized at Baseline (Visit 2).
Per-Protocol Set (PPS)	The PPS will include all mFAS patients who are not deemed noncompliant with treatment, who do not have any of the important protocol deviations that exclude patients from the PPS, and whose investigator site does not have significant GCP deviations that require a report to regulatory agencies. The important protocol deviations, including the subset that result in exclusion from the PPS, will be determined while the study team remains blinded, prior to the primary outcome database lock.
Randomized Withdrawal Population	All patients who enter the randomized withdrawal with non-missing SALT score at Week 52 will be included in the Randomized Withdrawal Population. They will be analyzed according to the IP to which they were randomized at Week 52.
Uptitration Population	All patients who are randomized to baricitinib 2-mg at baseline having SALT score >20 at Week 52 and were rescued to baricitinib 4-mg dose at Week 52. All patients need to take at least one dose of treatment and have non-missing SALT score on or after Week 52.
Retreated Population	A subset of patients who enter randomized withdrawal (randomized to placebo at Week 52) and were retreated with their baseline baricitinib dose at any time after experiencing loss of treatment benefit (SALT>20).
Safety Population	The safety population is defined as all randomized patients who receive at least 1 dose of investigational product (IP) and who did not discontinue from the study for the reason 'Lost to Follow-up' at the first postbaseline visit. Patients will be analyzed according to the IP to which they were assigned.

Abbreviations: AGA = androgenetic alopecia; GCP = good clinical practice; IP = investigational product.

a Some male patients with Grade IV AGA and female patients with patterned baldness may only be identified after hair regrowth on the scalp.

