To compare the maintenance of efficacy for patients randomized to remain on baricitinib, compared with patients randomized to placebo at Week 52 of the long-term extension period, as measured by physician-assessed signs of AA	
 
• Proportion of patients maintaining SALT <math>\leq 20</math> at Weeks 64, 76, 88, 104, 120, 136, 152, 168, 184, and 200
 
• Proportion of patients experiencing a loss of treatment benefit (<math>>20</math>-point absolute
 

	
worsening in SALT score) at Weeks 64, 76, 88, 104, 120, 136, 152, 168, 184, and 200.
 
 
Time to loss of treatment benefit (>20-point absolute worsening in SALT score)
 

For patients experiencing loss of treatment benefit after randomization to placebo at Week 52:
 
 
To evaluate the recapture of efficacy for patients who were retreated after experiencing a loss of treatment benefit during the long-term maintenance period as measured by physician-assessed signs of AA
 
To evaluate the recapture of efficacy for patients who were retreated after experiencing a loss of treatment benefit during the long-term maintenance period as assessed by PRO and quality of life tools
 
	
 
Proportion of patients that achieve a SALT <math>\leq 20</math> at 12, 16, 24, and 36 weeks of retreatment with baricitinib
 
Percent change in SALT score at 12, 16, 24, and 36 weeks of retreatment with baricitinib
 
Proportion of patients with a PRO for Scalp Hair Assessment score of 0 or 1 at 12, 16, 24, and 36 weeks of retreatment with baricitinib
 

Abbreviations: AA = alopecia areata; ClinRO = clinician-reported outcome; EB = eyebrow; EL = eyelash; HADS = Hospital Anxiety and Depression Scale; PRO = patient-reported outcome; SALT = Severity of Alopecia Tool; SALT50 = at least 50% improvement from Baseline in SALT score; SALT75 = at least 75% improvement from Baseline in SALT score; SALT90 = at least 90% improvement from Baseline in SALT score; SALT100 = 100% improvement from Baseline in SALT score.

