a Applicable to all patients at time of screening See EC [9] in protocol for treatments that will require washout.

b The maximal baricitinib dose for patients with renal impairment (defined as eGFR <60 mL/min/1.73 m^2) will be 2-mg QD (see Protocol).

- c At Week 36 patients in the placebo treatment arm who have NOT achieved SALT  $\leq 20$  will be rescued and re-randomized in a 1:1 ratio to baricitinib 2-mg or baricitinib 4-mg. All patients in the baricitinib treatment arms will continue in their current treatment arm regardless of treatment response at Week 36. Patients in the placebo arm who have achieved a SALT  $\leq 20$  will remain on placebo at Week 36. These patients who have experienced spontaneous regrowth on the scalp will remain on placebo for the remainder of the trial, even if relapse is observed later during the study.
- d At Week 52, responders (SALT  $\leq 20$ ) who are eligible (i.e., stayed on the same dose of baricitinib from initial randomization at Visit 2) will be randomized in a 3:1 ratio to either stay on their current dose of baricitinib or transition to placebo (randomized withdrawal).
- e Patients who have been in the baricitinib 4-mg treatment group from Baseline and who have never achieved a SALT  $\leq 20$  by Week 52 AND do not have a  $\geq 2$  point improvement in ClinRO Measure for Eyebrow or Eyelash Hair Loss (nonresponders) at Week 52 will be automatically transitioned to placebo. See footnote “f” for discontinuation criteria at Week 76.
- f Patients who are nonresponders (a SALT  $> 20$ ) at Weeks 52 AND 76 will be automatically discontinued from the study at Week 76, unless they have a  $\geq 2$ -point improvement from baseline in ClinRO Measure for Eyebrow or Eyelash Hair Loss. See Protocol for more details.
- g Responders who experience a loss of treatment benefit after Week 52 ( $> 20$ -point absolute worsening in SALT score) who were randomized to placebo at Week 52 (randomized withdrawal) will be retreated with their baricitinib dose, as randomized at Baseline (Visit 2). Patients who were randomized to remain on baricitinib (randomized withdrawal) will continue to receive the same dose of baricitinib. See Protocol for more details.

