### 4.11. Efficacy Analyses

The general methods used to summarize efficacy data, including the definition of baseline value for assessments are described in Section 4.2.

Efficacy analyses will generally be analyzed according to the following formats and patients will be analyzed according to the investigational product to which they were randomized at baseline, unless stated otherwise.

Table JAHO.4.6 includes the descriptions and derivations of the primary, secondary, and exploratory efficacy outcomes for Phase 2 and 3 portions.

Table JAHO.4.7 provides the detailed analyses for Phase 3 portion at the Week 36 primary outcome database lock including analysis type, method and imputation, population, time point, and comparisons for efficacy analyses.

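### Read literally, the randomized withdrawal population is grouped by Week 52 product only, which sets each dose arm beside a placebo group of mixed prior dose

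*SAP*

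**What the plan says.** SAP Section 4.1 says who enters the withdrawal phase: Week 52 responders "who have remained on the same dose of baricitinib from randomization (Visit 2) to Week 52, will enter the randomized withdrawal". That admits both 2-mg and 4-mg responders, and the section adds: "It is expected that there would be approximately 100 patients eligible for the randomized withdrawal". Footnote d to Figure JAHO.3.2 (Section 3.1.2) says that eligible responders "will be randomized in a 3:1 ratio to either stay on their current dose of baricitinib or transition to placebo (randomized withdrawal". Section 3.2 adds: "Randomization for the randomized withdrawal period will not be stratified".

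Table JAHO.4.1 then sets the grouping for this population: "They will be analyzed according to the IP to which they were randomized at Week 52". Section 4.11 has a general default, under which "patients will be analyzed according to the investigational product to which they were randomized at baseline, unless stated otherwise". Table JAHO.4.1 does state otherwise, so the default gives way here.

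The objective in Table JAHO.2.1 is "To compare the maintenance of efficacy for patients randomized to remain on baricitinib, compared with patients randomized to placebo at Week 52", with no dose named. The tables with withdrawal rows (JAHO.4.8 to 4.15, 4.18 and 4.19) give population, method and time point, and from 4.9 on the censoring rule. None of them mentions a split or adjustment by prior dose.

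**The concern.** The Week 52 step is in effect two parallel randomisations: 4-mg against 4-mg-to-placebo, and 2-mg against 2-mg-to-placebo. A former 2-mg responder could not have been assigned 4-mg at Week 52, nor a former 4-mg responder 2-mg. For everyone withdrawn, the Week 52 product is placebo whatever the earlier dose, so the stated rule discards the information that links each withdrawn patient to the correct stay arm.

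At stake is how maintained SALT ≤20, loss of treatment benefit, and the Kaplan-Meier curves for time to loss are read by dose. Set beside a mixed placebo curve, a dose-specific curve reflects both withdrawal and any difference in relapse course between patients coming off 4-mg and patients coming off 2-mg.

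**Working it through.** **1. Structure (no numbers needed).**

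| Baseline dose of responder | Possible Week 52 assignment | Group under Table JAHO.4.1 |
|---|---|---|
| 4-mg | 4-mg or placebo | 4-mg or placebo |
| 2-mg | 2-mg or placebo | 2-mg or placebo |

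Four combinations collapse to three groups, and only placebo is mixed.

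**2. Inputs, checked against the SAP's power statement.** Section 4.1 gives 625 Phase 3 patients and planning response rates of 30% (4-mg), 20% (2-mg) and 5% (placebo) at Week 36. Section 3.2 gives the 2:2:3 allocation.
- Arm sizes: 625 × 2/7 = 178.6 each for placebo and 2-mg; 625 × 3/7 = 267.9 for 4-mg.
- Power: above 99.9% for 4-mg at alpha 0.04; for 2-mg at alpha 0.01, 96.0% by normal approximation and 96.1% by exact Fisher enumeration. Both agree with the stated figure of more than 90%.

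**3. Expected entrants.**
- 4-mg: 267.9 × 0.30 = 80.4.
- 2-mg: 178.6 × 0.20 = 35.7.
- Total: 116.1, against the SAP's approximately 100. The ratio is 100/116.1 = 0.86, so about 14% fewer would close the gap. The SAP gives neither a Week 52 rate nor an attrition rate for its figure, so it can be neither confirmed nor faulted.

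**4. Make-up of the placebo group.** Former 4-mg share s = 80.4/116.1 = 0.69; former 2-mg share 1 − s = 0.31. With 100 eligible and a 3:1 split:
- 4-mg stay: 75 × 0.692 = 52; 4-mg to placebo: 25 × 0.692 = 17.
- 2-mg stay: 75 × 0.308 = 23; 2-mg to placebo: 25 × 0.308 = 8.

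This assumes Phase 3 entrants only, Week 36 rates carried to Week 52, and equal attrition by dose. Over assumed Week 52 rates of 30–40% (4-mg) and 20–30% (2-mg), s runs from 3×0.30/(3×0.30 + 2×0.30) = 60% to 3×0.40/(3×0.40 + 2×0.20) = 75%.

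**5. Effect on a dose-specific reading.** Let a be the loss-of-benefit rate off drug in former 4-mg patients, b the rate in former 2-mg patients, and d = b − a. The mixed placebo rate is s·a + (1 − s)·b, which equals a + (1 − s)d and also b − s·d.
- Beside the 4-mg arm, the reference is off by (1 − s)d = 0.31d.
- Beside the 2-mg arm, it is off by s·d = 0.69d, in the opposite direction.
- Over the range of s in step 4, the multipliers are 0.25 to 0.40 and 0.60 to 0.75.
- With d = 0, both errors are zero.

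**6. Both doses together against placebo.** The 3:1 ratio is the same for each dose, so the expected former 4-mg share is 52/75 = 69% among stayers and 17/25 = 69% on placebo. The comparison is balanced in expectation. Because allocation was not stratified, the actual placebo share can vary: drawing 25 from 100 with 69 former 4-mg patients gives a 95% hypergeometric range of 52% to 84%.

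**The case against.** The strongest reply is that pooling is inferred. The SAP never says that withdrawn patients from both doses form one column. The table shells are not in the documents, nor is the main protocol JAHO(e), to which the figure footnotes refer for detail; the protocol supplied is the open-label addendum, which has no withdrawal phase. A programmer could split by dose without contradicting the design. That is fair as far as it goes. But the grouping sentence is an explicit rule that displaces the baseline-product default, and its plain reading gives three groups.

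Second, the objective names baricitinib, not a dose, and step 6 shows that this contrast is sound in expectation. This stands. A reader might infer that the withdrawal comparison as a whole is non-randomised; the documents do not support that. Unequal mixing through unstratified allocation is chance variation, not bias.

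Third, these analyses are descriptive (Sections 4.2.3 and 4.11.5), outside the multiplicity scheme, and not sized to detect a difference (Section 4.1). This also stands, so type I error is not in question.

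Two further inferences fail. Section 4.2.3 allows region and episode duration to be left out of models for this population, but prior dose was never among those covariates, so the allowance neither causes nor worsens the mixing. The Retreated Population has no grouping rule of its own, so the Section 4.11 default to baseline product already covers it.

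**Conclusion.** The point holds for dose-specific readings. Followed literally, Table JAHO.4.1 places the 4-mg arm beside a placebo group of which about 31% could never have received 4-mg at Week 52, and the 2-mg arm beside one of which about 69% could never have received 2-mg. These shares rest on the SAP's Week 36 planning rates and the assumptions in step 4.

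The resulting distortion in response rates and in the loss-of-benefit curves is proportional to d. It is tempting to attach a figure in percentage points, or to argue that responding to the lower dose selects different patients. The documents give no relapse rate by prior dose, and both doses use the same SALT ≤20 criterion, so the size and direction of d are unknown and it may be zero. The consequence is limited to interpreting maintenance by dose in a descriptive secondary analysis.

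**What to change.** In Table JAHO.4.1, replace the grouping sentence for this population with: *Patients will be analysed by baseline dose and Week 52 assignment (4-mg/4-mg, 4-mg/placebo, 2-mg/2-mg, 2-mg/placebo).* Apply it only to the Randomized Withdrawal rows of Tables JAHO.4.8 to 4.15, 4.18 and 4.19, and to this population's Kaplan-Meier plots, with each stay arm shown beside its own withdrawal arm. Uptitration and Retreated rows in those tables stay as they are.

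Any overall baricitinib-versus-placebo difference should be stratified by baseline dose with size-based weights, for example Mantel-Haenszel. A simple average of the two within-dose differences would give half the weight to a stratum with only about 8 placebo patients.

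Baseline dose is already held for every patient, since it determines the dose on retreatment, so the work is SAP wording and table shells. The real cost is precision: about 17 and 8 placebo patients instead of 25 together, hence wider intervals. If the final lock has already passed, the four-group display can still be added to the study report, labelled as added after the lock.
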